### **SURGICAL DETAILS**

| GENERAL INFORMATION                                                                 |                                                                        |                                         |
|-------------------------------------------------------------------------------------|------------------------------------------------------------------------|-----------------------------------------|
| SUBJECT INITIALS:                                                                   | SURGERY DATE:  (DD-MMM-YYYY)  RF only if surgery is performed and subj | SUBJECT ID:  ect receives study device. |
| I. SURGICAL DETAILS                                                                 | ar only it surgery is performed and susj                               | ect receives study device.              |
| A. APPROACH Anterior/ Anterolateral Posterior/ Posterolateral Dual Incision Lateral |                                                                        | QUIRED?  C. NAVIGATION USED?  Yes  No   |
| D. INCISION LENGTH E. DURA                                                          | TION OF SURGERY                                                        | F. ESTIMATED BLOOD LOSS                 |
| cm Skin to                                                                          |                                                                        | сс                                      |
| II. PROSTHESIS                                                                      |                                                                        |                                         |
| G. PROSTHESES -                                                                     | H. OTHER?                                                              |                                         |
| Upload a PDF copy of the component label(s) in                                      | nplanted. *If Yes, specify                                             | and attach a copy of the label(s):      |
| Please go to Subject Information screen and en in Products tab.                     | Reset                                                                  | her (Specify) Reference # Lot #         |
| Acetabular Shell                                                                    | X                                                                      |                                         |
| Acetabular Insert                                                                   |                                                                        |                                         |
| Femoral Bearing Head                                                                |                                                                        |                                         |
| Modular Neck                                                                        |                                                                        |                                         |
| Modular / Femoral Stem                                                              |                                                                        |                                         |
| I. INTRAOPERATIVE COMPLICATION?                                                     | J. DISCHARGED                                                          | TO: (Check One)                         |
| *If Yes, complete AE form. \( \sum \text{Yes*} \) No                                | Skilled Nurs                                                           | ing Facility                            |
|                                                                                     | Chronic Care                                                           | e Center                                |
|                                                                                     | Rehabilitation                                                         | on Unit                                 |
|                                                                                     | Home                                                                   |                                         |
|                                                                                     | Other: (Spec                                                           |                                         |
|                                                                                     | Discharge D                                                            | DD-MMM-YYYY                             |
| III. COMMENTS                                                                       |                                                                        |                                         |
|                                                                                     |                                                                        |                                         |
|                                                                                     |                                                                        |                                         |
| Reason for Save                                                                     |                                                                        |                                         |
| Verification / Confirmation Method                                                  |                                                                        |                                         |
|                                                                                     | 6.4.                                                                   |                                         |

Page 1 of 1

## Restoration®ADM X3®Acetabular System POST-OP FUNCTIONAL EVALUATION

| GENERAL INFORMATION                                                       |                                                                                                                                                                      |                                      |                                       |  |  |  |  |  |  |  |
|---------------------------------------------------------------------------|----------------------------------------------------------------------------------------------------------------------------------------------------------------------|--------------------------------------|---------------------------------------|--|--|--|--|--|--|--|
| SUBJECT INITIALS:                                                         | VISIT DATE:                                                                                                                                                          | VISIT:                               | SUBJECT IDENTIFIER:                   |  |  |  |  |  |  |  |
|                                                                           |                                                                                                                                                                      |                                      |                                       |  |  |  |  |  |  |  |
| I. PAIN                                                                   | (DD-MMM-YYYY)                                                                                                                                                        |                                      |                                       |  |  |  |  |  |  |  |
| A. PAIN None, or ignores it                                               |                                                                                                                                                                      |                                      |                                       |  |  |  |  |  |  |  |
| Slight, occasional, n                                                     | o compromise in activities                                                                                                                                           |                                      |                                       |  |  |  |  |  |  |  |
| Mild, no effect on a                                                      | verage activities, rarely mo                                                                                                                                         | derate pain with unusual activity, n | nay take aspirin                      |  |  |  |  |  |  |  |
| ( )                                                                       | Moderate pain, tolerable but makes concessions to pain. Some limitations of ordinary activity or work.  May require occasional pain medication stronger than aspirin |                                      |                                       |  |  |  |  |  |  |  |
| Marked pain, seriou                                                       | Marked pain, serious limitation of activities                                                                                                                        |                                      |                                       |  |  |  |  |  |  |  |
| Totally disabled, crippled, pain in bed, bedridden                        |                                                                                                                                                                      |                                      |                                       |  |  |  |  |  |  |  |
| II. FUNCTION / GAIT                                                       |                                                                                                                                                                      |                                      |                                       |  |  |  |  |  |  |  |
| B. LIMP                                                                   | C. SUPPORT                                                                                                                                                           |                                      | D. DISTANCE WALKED                    |  |  |  |  |  |  |  |
| None                                                                      | ○ None                                                                                                                                                               |                                      | 

Unlimited

           |  |  |  |  |  |  |  |
| ○ Slight                                                                  | Cane, long v                                                                                                                                                         | valks                                | Six blocks                            |  |  |  |  |  |  |  |
| Moderate                                                                  | Cane, most                                                                                                                                                           | of the time                          | 

Two or three blocks

 |  |  |  |  |  |  |  |
| Severe or unable to walk                                                  | One crutch                                                                                                                                                           | Indoors only                         |                                       |  |  |  |  |  |  |  |
|                                                                           | Two canes                                                                                                                                                            |                                      | 

Bed and chair only

  |  |  |  |  |  |  |  |
|                                                                           | Two crutche                                                                                                                                                          | es, walker or unable to walk         |                                       |  |  |  |  |  |  |  |
| III. FUNCTIONAL ACTIVITIES                                                |                                                                                                                                                                      |                                      |                                       |  |  |  |  |  |  |  |
| E. STAIRS                                                                 | F. SOCKS / SHOES                                                                                                                                                     | G. SITTING                           | H. PUBLIC TRANSPORTATION              |  |  |  |  |  |  |  |
| Normally without using a rail                                             | With ease                                                                                                                                                            | Any chair, 1 hour                    | Able to use                           |  |  |  |  |  |  |  |
| Normally using a railing                                                  | ○ With difficulty                                                                                                                                                    | High chair, 1/2 hour                 | Not able to use                       |  |  |  |  |  |  |  |
| O In any manner                                                           | ○ Unable                                                                                                                                                             | Unable to sit comfortably in a       | -                                     |  |  |  |  |  |  |  |
| Unable to use stairs                                                      |                                                                                                                                                                      |                                      |                                       |  |  |  |  |  |  |  |
|                                                                           |                                                                                                                                                                      |                                      |                                       |  |  |  |  |  |  |  |
| I. ABSENCE OF DEFORMITY (O
Select "Yes" to indicate there is no deform |                                                                                                                                                                      | J. RANGE OF MOTIOI is a deformity.   | (Operative side only)                 |  |  |  |  |  |  |  |
| Fixed flexion contracture < 30°                                           | $\circ$                                                                                                                                                              | Permanent (Fixed) Flex               | ion                                   |  |  |  |  |  |  |  |
| Fixed adduction < 10°                                                     | 0 0                                                                                                                                                                  | Flexion to                           | •                                     |  |  |  |  |  |  |  |
| Fixed internal rotation in extensio                                       | n < 10°                                                                                                                                                              | Abduction to                         | •                                     |  |  |  |  |  |  |  |
| Leg length discrepancy < 3.2 cm                                           | 0 0                                                                                                                                                                  | Adduction to                         | •                                     |  |  |  |  |  |  |  |
|                                                                           | discrepancy exists                                                                                                                                                   | External Rotation in Ext             | tension to °                          |  |  |  |  |  |  |  |
| record 0 cm ar                                                            | d check Yes.                                                                                                                                                         | Internal Rotation in Ext             | ension to °                           |  |  |  |  |  |  |  |

HHS

Auto Calculate Read Only

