# **Objectives**

Objectives	An additional Follow-Up Questionnaire will be administered annually in postoperative years 6-10 to assess patient satisfaction and pain, and to capture adverse events. This questionnaire will provide the survivorship information necessary to evaluate the primary objective of the study.  To review radiographic stability and complications between those implanted with the Restoration® ADM X3® Acetabular System and published results for other primary hip systems. Complication rates for psoas impingement and associated groin pain will be reviewed, as applicable.				
Number of Cases	Cases will be enrolled until 350 cases have received the Restoration ADM® X3® Acetabular System.  Additionally, a minimum of 100 cases (within the study population) will receive the Accolade® II Hip Stem.				

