In a dual mobility system the femoral head rotates within the polyethylene acetabular insert as with traditional designs, with the exception that during extended ROM, the UHMWPE insert is able to rotate within the cup. This configuration allows improved ROM before impingement. One reason for groin pain postoperatively is the conflict of the anterior rim of the acetabular cup and the ilio-psoas tendon. Tracol et al. evaluated the in vitro depth of the psoas ilio-pubic notch and developed the Restoration® ADM cup with a 3.5 mm anterior notch. The anterior cutout is designed to mitigate conflict of the anterior portion of the cup and the psoas tendon.

The polyethylene insert utilized in the Restoration® ADM X3® Acetabular System is composed of X3® sequentially annealed UHMWPE. D'Antonio et al.¹⁰ presented clinical data from 246 cases in a prospective multicenter study (Trident® X3® Acetabular Insert Study) in which all patients received X3® polyethylene inserts. The X3® inserts had a low linear wear rate of 0.008 mm/year at 5 years which represents a 58% improvement over a first-generation annealed highly cross-linked polyethylene.

Cementless acetabular components for THA became popular in the United States in the early 1980s, primarily due to poor long-term results with cemented cups. Superior radiographic performance has been reported for cementless cups as compared with cemented fixation. The design of the Restoration® ADM Acetabular Shell is based on the Trident® PSL cementless cup. The cup is manufactured from wrought cobalt chromium alloy. The acetabular shell has a CP Titanium plasma sprayed and HA coating to establish initial good fixation. HA is a naturally occurring mineral form of calcium apatite that comprises 70% of human bone. HA is currently used as a biological coating on a variety of orthopaedic implants to stimulate bone ongrowth.

HA coating has over 15 years of published clinical history of use on the femoral stem showing 95.3% survivorship. The coating is designed to provide a roughened surface texture. It is not an ingrowth surface but rather provides a surface roughness to the component.

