# 2.1.2 Secondary

The secondary objectives of this study will be to evaluate all-cause revision and removal rates with the Restoration® ADM X3® Acetabular System and compare with those reported for other primary hip systems in the literature.

Additionaly, psoas impingement and associated groin pain, function and health-related QOL between the Restoration® ADM X3® Acetabular System and those reported in the literature for other primary hip systems and similar dual mobility cups on the market will be compared at postoperative time points.

Lastly, radiographic stability and complications between those implanted with the Restoration® ADM X3® Acetabular System and other primary hip systems in the literature will be reviewed.

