# 9.2 Safety Parameters

# 9.2.1 Safety Parameters

Safety parameters will include

- All AEs reported
- Rate of psoas impingement
- Rate of associated groin pain (derived from the 'Operative Site Other' field on the AE form)

- Radiographic stability at each postoperative visit
- Revision or removal of any study component
- Revision or removal of the Restoration® ADM Acetabular Shell and X3®
   Acetabular Insert

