### 9.2.2 Safety Analysis

All AEs will be listed, tabulated and summarized by event, number and percent of cases/subjects. AE rates and 95% confidence intervals will be presented.

For categorical variables, such as radiographic stability, the number and percent in each category will be presented.

The Kaplan-Meier survival curve of revision/removal of any study component and the Restoration® ADM Acetabular Shell and X3® Acetabular Insert will also be displayed.

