### **FOLLOW-UP QUESTIONNAIRE**

| GENERAL INFORMATION                                                                                               |                                         |             |            |  |  |  |
|-------------------------------------------------------------------------------------------------------------------|-----------------------------------------|-------------|------------|--|--|--|
| SUBJECT INITIALS:                                                                                                 | VISIT:                                  | SUBJECT ID: |            |  |  |  |
|                                                                                                                   |                                         |             |            |  |  |  |
|                                                                                                                   | QUESTIONNAIRE COMPLETED BY: Vis         | sit O M     | lail Phone |  |  |  |
| I. HIP QUESTIONS                                                                                                  | QUESTIONNAINE COMITETED BY:             | 310 0 10    | ian Thoric |  |  |  |
|                                                                                                                   |                                         | _           | _          |  |  |  |
| 1. Do you have any pain in your hip that has the stu
Subject comment:                                          | dy hip replacement?                     | YES         | O NO       |  |  |  |
| Subject comment.                                                                                                  |                                         |             |            |  |  |  |
|                                                                                                                   |                                         |             |            |  |  |  |
|                                                                                                                   |                                         |             |            |  |  |  |
| Coordinator comment:                                                                                              |                                         |             |            |  |  |  |

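### The planned groin pain rate counts only free text under the AE form's operative-site Other field, and no visit form asks where pain is, so groin pain will probably be under-counted

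*Combined protocol and SAP*

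**What the plan says.** Section 2.1.2 lists the outcome among its secondary objectives: "Additionaly, psoas impingement and associated groin pain, function and health-related QOL between the Restoration® ADM X3® Acetabular System" and published systems "will be compared at postoperative time points". The synopsis is softer: "Complication rates for psoas impingement and associated groin pain will be reviewed, as applicable". Section 9.2.1 lists two separate safety parameters, psoas impingement and "Rate of associated groin pain (derived from the 'Operative Site Other' field on the AE form". Section 9.2.2 gives the analysis: "AE rates and 95% confidence intervals will be presented".

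The background (section 1.1) explains why the outcome matters for this shell: "One reason for groin pain postoperatively is the conflict of the anterior rim of the acetabular cup and the ilio-psoas tendon". The anterior cut-out is there to reduce that conflict.

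Three forms in Appendix F bear on the point:

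- The Post-Op Functional Evaluation, item A, offers six grades of pain severity, one of which reads "Moderate pain, tolerable but makes concessions to pain. Some limitations of ordinary activity or work". It has no location field.
- The Follow-Up Questionnaire for years 6 to 10, item 1, begins "1. Do you have any pain in your hip that has the stu" (the line breaks there in the extracted text) and is answered yes or no. Comment boxes for the subject and the coordinator follow.
- The Adverse Event form asks for one event. Hip Pain, Thigh Pain and Iliopsoas Tendon Impingement are check boxes. Groin pain is not, and would be written in under Other.

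**The concern.** Groin pain is the symptom that the protocol itself links to the cut-out's purpose. Its rate depends on a site choosing Other and writing the word groin, on a form where three ready-made boxes could each describe the same complaint. A case entered under one of those boxes is a recorded operative-site event, but the section 9.2.1 derivation does not count it. If the visit forms asked where the pain was, such cases could be found afterwards. They do not ask.

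At stake is whether the number set against the literature measures how often groin pain occurred, or how often sites chose one field over another.

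**Working it through.** The documents give no groin pain rate, so there is no figure to reproduce. The check follows the outcome from objective to data field.

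1. **Objective to parameter.** Section 2.1.2 (comparison at postoperative time points) leads to section 9.2.1 (rate from the operative-site Other field) and then to section 9.2.2 (AE rates with 95% intervals). The chain is complete, and it has a single data source.

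2. **Parameter to form.** The AE form instructs the site to check one event. A subject with groin pain can be entered in at least four ways:
   - Other, with groin written in: counted.
   - Hip Pain: not counted.
   - Thigh Pain: not counted.
   - Iliopsoas Tendon Impingement: counted as impingement, not as groin pain.

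   The last route matters most for pain described as associated with impingement. Section 8.1, on the AE reporting period, tells sites to group clearly related signs and symptoms under one diagnosis in the source record, as appropriate. A site that does this would reasonably tick the impingement box, and the associated groin pain then drops out of its own rate.

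3. **Can missed cases be recovered?** The AE form has a narrative item on the circumstances and symptoms, and the questionnaire has comment boxes. Either might mention the groin, but nothing requires it, so silence cannot be read as absence. The Post-Op Functional Evaluation gives severity only, and the questionnaire tick gives presence only. Recovery would be partial and would differ between sites.

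4. **What the planned source can give.** The AE form carries an onset date and a resolved or unresolved date. These support the number and percent of cases with a groin pain AE, incidence by follow-up interval, and the share with an open groin pain AE at a given visit.

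5. **What it cannot give.** It cannot give the proportion of subjects with groin pain among all who were asked about location at a visit, because no form asks.

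6. **Size.** Let p be the true proportion of cases with a reportable groin pain event, and c the share of those entered under Other with the groin named. The reported rate is then p × c and the shortfall is p × (1 − c). The documents give neither p nor c, so the shortfall cannot be computed. The unit effect can: with all 350 enrolled cases (section 3.3) in the denominator, each case entered elsewhere lowers the rate by 1/350 = 0.29 percentage points.

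**The case against.** The best defence is that the plan never meant to take groin pain from the visit pain items. The synopsis calls it a complication rate and section 9.2.1 lists it as a safety parameter, so an AE source fits that intent. Section 2.1.2 names no visits and does not define a by-visit prevalence. AE collection is also active: section 8.1 requires specific questioning at each contact and makes every operative-site AE reportable whatever its seriousness. Item K of the Post-Op Functional Evaluation asks about protocol-defined AEs since the last visit. In years 6 to 10 the coordinator must review all answers for an AE and follow up questionable ones.

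Most of this stands, and it rules out three stronger readings that a reader might infer:

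- **That no groin pain rate can be produced at any visit.** This is wrong. The AE form is the named source and its records are dated.
- **That groin pain is recorded only if raised unprompted.** This is also wrong. AEs are asked about at each contact; what is missing is a prompt that names the groin.
- **That the resulting bias favours the cut-out design, by a stated number of points.** That would need the true rate, the share captured, and how the published rates were collected. The documents give none of these. If the published figures are also complication reports, the direction is unknown.

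It is also fair to call a by-visit proportion from direct questioning a design preference. The defence does not, however, answer the filing problem. Good questioning can produce an AE form for every subject with groin pain and still leave some of them out of the rate, because section 9.2.1 reads one field of that form.

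**Conclusion.** The point holds in a limited form. Followed as written, the plan will produce a groin pain rate, and it will probably be too low because competing check boxes take cases away from the only field that is counted. The visit forms cannot reliably restore those cases, and no systematically elicited by-visit proportion will exist for the section 2.1.2 comparison. The size of the under-count and its direction relative to the literature cannot be determined from the documents.

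This rests on one assumption: that some sites will enter groin pain under Hip Pain, Thigh Pain or Iliopsoas Tendon Impingement. If every site wrote it under Other, the AE rate would be sound, though there would still be no elicited proportion. The primary endpoint is untouched. This is a secondary and safety outcome that should be corrected because it speaks to the purpose of the cut-out and visits passed without the item cannot be recovered.

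**What to change.** Add one pain-location item (groin, thigh, lateral, buttock, other; tick all that apply), shown when pain is present, in two places:

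- on the Post-Op Functional Evaluation after item A, outside the Harris Hip Score calculation, so that the score is unchanged;
- on the Follow-Up Questionnaire at item 1.

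State in sections 9.2.1 and 9.2.2 that the proportion with groin pain will be reported at each remaining visit with a 95% confidence interval, among subjects who completed the form at that visit. For years 6 to 10, use the questionnaire as the source, since it is required of all subjects while the functional evaluation at years 7 and 10 is optional. Keep the AE-derived complication rate and show it beside the new figure, with a note that it counts only entries under Other.

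The cost is a small eCRF change on two existing forms and one added table. Visits already completed will lack the item, so the by-visit series will start partway through follow-up.
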